5.1 Data Summaries for COVID-19

TEAEs related to a COVID-19 infection will be summarized using the check box on the CRF page by treatment arm separately from other TEAEs. Deaths related to COVID-19 will be summarized or listed by treatment arm separately from deaths unrelated to COVID-19. COVID-19 laboratory tests will be listed by treatment arm.

5.2 Safety Run-in

Safety data for Safety Run-in subjects treated with study treatment will be summarized and/or listed by the TLS risk category at baseline (Low versus Increased) separately from the randomized subjects.

Page 30 of 35

In addition to standard safety summaries for TEAEs, SAEs, Grade 3 or higher TEAEs, TEAEs leading to study drug discontinuation, and TEAEs leading to death, the summary of safety data included will be limited in scope to DLTs and TLS.

6 TREATMENT-NAÏVE COHORT

The following data will be summarized for treatment-naïve subjects who were enrolled into the study at the time of the primary PFS analysis for subjects with R/R MCL. Data summaries will be limited to the followings:

- Demographics and baseline characteristics
- Study drug exposure
- Treatment disposition and subject disposition
- Treatment-emergent adverse events

A comprehensive and complete data summary and analysis for treatment-naïve subjects will be described in an SAP addendum at the appropriate time prior to primary analysis.

7 CHANGES IN THE PROTOCOL-PLANNED ANALYSES

- 1. In alignment with the FDA guidance (Statistical Considerations for Clinical Trials During the COVID-19 Public Health Emergency, June 2020), in order to mitigate the potential impact on key efficacy endpoints due to COVID-19, the follow-up will be extended to accrue more events as described in Section 1.5.1 and Section 1.5.2 over the originally planned event numbers (134 events for PFS and 155 events for OS).
- 2. Change superiority boundary for the interim OS analysis from O'Brien Fleming boundary to Haybittle-Peto boundary.
- 3. Specify secondary and exploratory endpoints to be included in the CSR.
- 4. IRC will be implemented to do the overall disease assessment based on Cheson 2014 (Lugano Classification Criteria). A sensitivity analysis will be conducted for PFS using the IRC assessment.
- 5. Since only 9 subjects in total were randomized to the stratum of ECOG performance status of 2, stratification by the three randomization stratification factors will lead to empty or very small strata. Therefore, all stratified tests/analyses will only be based on two randomization stratification factors per IRT: prior lines of therapy (1-2 vs ≥ 3) and TLS risk category (low risk vs. increased risk).
- 6. The CR rate and ORR will be compared by rate ratio between the two treatment arms using CMH chi-square test stratified by the two randomization stratification factors instead of by the difference in proportion between the two treatment arms.
- 7. The MRD-negative remission rate for CR subjects evaluable for MRD will be compared by Fisher's Exact test due to the small sample size.

8 APPENDICES

8.1 Algorithm for Defining 2 or more Consecutive Assessments Prior to the PFS Event

This study has 3 planned imaging schedules: every 12 weeks in the first year, every 16 weeks in the second and third years, and every 24 weeks afterwards. The exact imaging schedules are defined in weeks (see Table 2). Based on the change between the schedules, two transitions of the imaging schedule are described as follows:

- 1. When the last non-PD assessment occurs at Week 37, the next assessment is planned at Week 49 (12 weeks from Week 37) and then at Week 65 (16 weeks from Week 49).
- 2. When the last non-PD assessment occurs at Week 129, the next assessment is planned at Week 145 (16 weeks from Week 129) and then at Week 169 (24 weeks from Week 145).

This algorithm has two steps in series:

- 1. Step 1 (Columns 2-4 of Table 1): To map the last adequate non-PD assessment to a closest scheduled visit based on the study day of the last adequate non-PD assessment using the midpoint window (see footnote of Table 1 for details). Once the assessment is mapped to a scheduled visit, the imaging interval for the next two subsequent consecutive visits can be decided based on the planned imaging schedule.
- 2. Step 2 (column 5 of Table 1): Calculate maximum days allowed for those two subsequent visits based on the planned imaging interval plus 7 days based on the protocol-specified window (+/- 7 days) for each visit.

There are five time periods in Table 1 based on three planned imaging schedules and two transitions in the imaging schedule.

Table 1: Algorithm for defining missing two or more consecutive assessments prior to the PFS events

Time			Imaging Schedule for the Two Subsequent	Maximum Gap& in Days
Period	Last Adequate Non-PD Assessment		Consecutive Assessments	Allowed between PFS
			after the Last Adequate Non-PD Assessment	Event and Last Adequate
	Scheduled Visit	Study Day*		Non-PD Assessment
1	Week 13-Week 25	Day 2- Day 211	12 weeks (84 days)	182=(84+7)*2
2	Week 37	Day 212 - Day 295	12 weeks (84 days) &16 weeks (112 days)	210=(84+7) + (112+7)
3	Week 49-Week 113	Day 296 – Day 841	16 weeks (112 days)	238=(112+7)*2
4	Week 129	Day 842 - Day 953	16 weeks (112 days) & 24 weeks (168 days)	294=(112+7) + (168+7)
5	Week 145 and higher	Day 954 and higher	24 weeks (168 days)	350=(168+7)*2

^{*:} The visit window for each visit is based on the midpoint between two scheduled visits (i.e. target day +/- half of the planned interval between two scheduled visits). However, start day of Week 13 is one day after randomization (Day 2). If the last adequate non-PD assessment is the same as or earlier than the midpoint, it will be assigned to the earlier visit, and if the assessment is later than the midpoint, it will be assigned to the later visit. Study day is calculated in reference to the randomization date.

[&]amp;: A 7-day window is allowed per the protocol for each subsequent visit.

Visits sharing the same imaging schedules are combined in Time Periods 1, 3, and 5, respectively; details are displayed in Table 2.

Detailed imaging schedules (by weeks) and the target day, start day, and end day of each scheduled visit along with the maximum gap in days allowed between the PFS event and the last adequate non-PD assessment are displayed in Table 2 below. Each of the five time periods is highlighted in a different color in Table 2.

Table 2: Protocol Imaging Schedule

Interval from the Previous Scheduled Visit	Scheduled Visit	Target Study Day (Start Day – End Day)* of Each Visit	Start Day - End Day (of the Time Period)	Maximum Gap ^{&} in Days Allowed between PFS Event and Last Adequate Non-PD Assessment
12 weeks=84 days	WEEK 13	D85 (D2-D127)	D2-D211 (Week 13-Week 25)	(84+7)*2=182
	WEEK 25	D169 (D128-D211)		
	WEEK 37	D253 (D212-D295)	D212-D295 (Week 37)	(84+7)+(112+7)=210 Note: Two consecutive assessments after Week 37 are at the interval of 12 and 16 weeks (at Weeks 49 & 65, respectively)
	WEEK 49	D337 (D296-D393)	D296-D841(Week 49-Week	(112+7)*2=238
16 weeks=112 days	WEEK 65	D449 (D394-D505)	113)	
	WEEK 81	D561 (D506-D617)		
	WEEK 97	D673 (D618-D729)		
	WEEK 113	D785 (D730-D841)		
	WEEK 129	D897 (D842-D953)	D842-D953 (Week 129)	(112+7)+(168+7)=294 Note: Two consecutive assessments after Week 129 are at the interval of 16 and 24 weeks (at Weeks 145 & 169, respectively)
	WEEK 145	D1009 (D954-D1093)	All visits (Week 145 and	(168+7)*2=350
24 weeks=168 days	WEEK 169	D1177 (D1094-D1261)	Higher) after D953 are in this	
	WEEK 193	D1345 (D1262-D1429)	time period	
	WEEK 217	D1513 (D1430-D1597)		
	WEEK 241	D1681 (D1598-D1765)		

^{*:} End day and start day of each scheduled visit are based on the midpoint window (i.e. target day +/- half of the interval between two scheduled visits). However, start day of Week 13 is one day after randomization (Day 2). If the last adequate non-PD assessment is the same as or earlier than the midpoint, it will be assigned to the earlier visit, and if the assessment is later than the midpoint, it will be assigned to the later visit. Study day is calculated in reference to the randomization date. &: A 7-day window is allowed per the protocol for each subsequent visit.

Page 35 of 35

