EOT = End-of-Treatment Visit; RFU = Response Follow-up Visit; LTFU = Long-term Follow up; PRO = patient-reported outcome;

Footnotes:

- ^a After week 13, study drug dispensing visits are scheduled every 4 weeks for one year; every 8 weeks during the 2nd and 3rd years; and every 12 weeks thereafter until treatment discontinuation.
- b Response assessment visits are scheduled on Week 13 Day 1 (±7 days); every 12 weeks for the remainder of the 1st year; every 16 weeks during the 2nd and 3rd years, and every 24 weeks thereafter until PD. In addition, response assessments can be performed as clinically indicated to confirm response or progression.
- ^c An EOT visit will occur 30 days (±7) from the last dose of study drug or prior to the start of a new anticancer treatment.
- d Subjects who discontinue for reasons other than PD will have follow-up response assessments (based on Week 1 Day 1 for a subject) every 12 weeks (± 14 days) from the 1st dose for the 1st year; every 16 weeks (± 14 days) during the 2nd and 3rd years; and every 24 weeks (± 14 days) thereafter until PD.
- ^e Concomitant medications are collected from 30 days before the first dose through the 30 days after the last dose of study drug.
- f See Section 11 for details regarding the reporting of AEs.
- g A complete physical examination (at Screening and EOT) will include, at a minimum, the general appearance of the subject, height (may use prior height measurement if available in source documents) and weight, and examination of the skin, eyes, ears, nose, throat, lungs, heart, abdomen, extremities, musculoskeletal system, lymphatic system, and nervous system. At other timepoints, a limited symptom-directed physical exam will be performed. The physical exam should include an eye-related symptom assessment.
- h Vital signs (blood pressure, heart rate, and body temperature) will be assessed after the subject has rested in the sitting position for ≥ 3 minutes.
- ⁱA single 12-lead ECG will be done at Screening and at the EOT visit. Subjects should be in a supine position and resting for at least 10 minutes before obtaining the ECG. During the treatment period, ECG's may be performed at the investigator's discretion, particularly in subjects with arrhythmic symptoms (eg, palpitations, lightheadedness) or new onset dyspnea.

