1) To address the intercurrent events of use of subsequent anticancer therapy, hypothetical strategy (subjects who received subsequent anti-cancer treatment will be censored at the last adequate post-baseline disease assessment showing no evidence of PD prior to the initiation of subsequent anti-cancer treatment) is implemented.
2) Subjects who missed two or more consecutive overall disease assessments (algorithm is described in Appendix 1) prior to the PFS event will be censored at the last adequate post-baseline disease assessment showing no evidence of PD prior to the first missed disease assessment.
3) Implement the two censoring conventions from items 1) and 2) above. This will be the primary analysis only for the US regulatory consideration.
4) Analyses listed under Primary Analysis and Sensitivity/Supplementary Analyses items 1) - 3) will be repeated for the IRC assessment.
5) To address the intercurrent events of COVID-19 deaths, hypothetical strategy (Pre-PD deaths due to COVID-19 are censored) is implemented.
6) Unstratified log-rank test and unstratified Cox regression model to calculate HR and its 2-sided 95% CI; same censoring convention as the primary analysis.
Subgroup Analysis: Hazard ratio and its 95% CI from unstratified Cox regression model for each subgroup. Same censoring convention as for the primary analysis.
For the US, additional censoring conventions as specified for the US primary PFS analysis in item 3) above will be implemented.

Efficacy Endpoint	Definition	Analysis Method			
Secondary Endpoints					

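### The missed-visit rule in the US primary PFS analysis assumes a 7-day window for every scan, but the protocol allows 14 days in response follow-up, so it can censor an in-window progression after one missed visit

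*SAP*

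**What the plan says.** SAP Section 4.2, Table 2, item 2 applies to "Subjects who missed two or more consecutive overall disease assessments" before the PFS event and censors them at the last adequate assessment before the first missed one. Item 3 combines this with censoring at subsequent anti-cancer therapy and adds: "This will be the primary analysis only for the US regulatory consideration". The same censoring carries into the US subgroup analyses and the US versions of duration of CR and duration of response. Item 4 repeats the analyses on independent review.

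Appendix 8.1 puts the rule into practice. Step 1 maps the last adequate scan without progression to a scheduled visit, which fixes the two imaging intervals that follow. Step 2 reads: "Calculate maximum days allowed for those two subsequent visits based on the planned imaging interval plus 7 days based on the protocol-specified window" of ±7 days. The result is the "maximum gap in days allowed between the PFS event and the last adequate non-PD assessment". The footnotes to both appendix tables say: "A 7-day window is allowed per the protocol for each subsequent visit".

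Protocol Appendix A has two windows. The response assessment column carries ±7 days. The response follow-up column carries ±14 days, and footnote d sets those visits at "every 12 weeks (± 14 days) from the 1st dose for the 1st year", with the same ±14 days on the later 16- and 24-week schedules. Protocol Section 8.3.1 places in response follow-up every subject who stops treatment for a reason other than progression.

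**The concern.** The SAP attributes to the protocol a window that the protocol gives only for on-treatment assessments. SAP Section 1 lets the SAP override the protocol and promises that changes are recorded in Section 7. Section 7 does not list this one, and the appendix presents the 7 days as following the protocol. It reads as an oversight, not a choice.

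The rule decides which progressions count as events in the US primary analysis. If the limit is shorter than the gap that the protocol's own windows permit after one missed visit, a subject whose two scans were both in window can lose a genuine event under a rule meant for two missed visits.

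**Working it through.** **Inputs.** Intervals of 84, 112 and 168 days and target days from SAP Appendix 8.1, Tables 1 and 2; windows of ±7 days (on treatment) and ±14 days (response follow-up) from Protocol Appendix A; about 150 PFS events from SAP Section 1.5.1; target HR 0.61 from SAP Section 1.4.1.

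**Reproducing the limits.** Let I be the sum of the two intervals after the mapped visit. The SAP limit is I + 7 + 7. All five limits reproduce.

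**Largest gap with one missed visit and both scans in window.** Let x be the last scan's deviation from its target day and y the progression scan's deviation from its own. The gap is I + y − x, so the event is censored when y − x > 14. The largest gap is I + 14 if both scans are on treatment, I + 7 + 14 = I + 21 if only the progression scan is in follow-up, and I + 14 + 14 = I + 28 if both are.

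| Last adequate scan | I | SAP limit and on-treatment maximum (I + 14) | Only PD scan in follow-up (I + 21) | Both in follow-up (I + 28) |
|---|---|---|---|---|
| Weeks 13–25 | 84 + 84 = 168 | 182 | 189 | 196 |
| Week 37 | 84 + 112 = 196 | 210 | 217 | 224 |
| Weeks 49–113 | 112 + 112 = 224 | 238 | 245 | 252 |
| Week 129 | 112 + 168 = 280 | 294 | 301 | 308 |
| Week 145 on | 168 + 168 = 336 | 350 | 357 | 364 |

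On treatment the largest compliant gap equals the limit, so nothing is wrongly censored. With follow-up scans the excess is up to 7 or 14 days.

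**Example.** Week 25 has target Day 169, so a follow-up scan on Day 155 is in window (169 − 14). Week 37 is missed. Week 49 has target Day 337, so progression on Day 351 is in window (337 + 14). The gap is 351 − 155 = 196 > 182, and the event is censored. With the last scan on target and progression 14 days late, the gap is 168 + 14 = 182 and the event is kept.

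**How often the drift exceeds 14 days.** Giving every in-window pair of days equal weight (an assumption):

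- both on treatment: 0 of 15 × 15 = 225 pairs
- only the progression scan in follow-up: 7 + 6 + … + 1 = 28 of 15 × 29 = 435 pairs (6.4%)
- both in follow-up: 14 + 13 + … + 1 = 105 of 29 × 29 = 841 pairs (12.5%)

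**Events at risk.** The documents do not say how many progressions are found off treatment after exactly one missed visit. Suppose 2%, 5% or 10% of 150:

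- 3 events: 3 × 28/435 = 0.2 to 3 × 105/841 = 0.4 wrongly censored
- 7.5 events: 0.5 to 0.9
- 15 events: 1.0 to 1.9

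**Power.** By Schoenfeld's formula at HR 0.61 and one-sided 0.025, power is 85.7% with 150 events and 85.2% with 148.

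**The case against.** The strongest reply is that the affected set is very narrow. The subject must be off treatment, have missed exactly one visit, and then progress with more than 14 days of combined drift. US item 1 already censors follow-up subjects who start new therapy, apart from responders given transplant or cellular therapy, which the SAP does not count as such. The other regions' primary analysis does not use the rule, and items 1, 2 and 3 are run separately, so its influence will be visible. All of this stands and limits the size of the point. It does not make the statement about the protocol correct.

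A reader might also infer that measuring from the actual scan date, after mapping that scan to a visit, is itself an error. A scan on Day 128 maps to Week 25; with Week 37 missed and progression on Day 337, the gap is 337 − 128 = 209 > 182. But Day 128 is 41 days before the Week 25 target, outside both Days 162–176 and Days 155–183. By protocol windows Weeks 25 and 37 were both unobserved, so censoring is arguably what item 2 intends. Counting from the mapped target day has its own failure. A scan on Day 211 also maps to Week 25, the cutoff would be 337 + 7 = Day 344, and progression on Day 345 would be censored after 345 − 211 = 134 days, although by the same mapping only Week 37 was missed. The SAP rule keeps that event. The origin of the gap is a choice between approximations.

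**Conclusion.** The window is wrong for response follow-up scans, and the rule can therefore censor a protocol-compliant progression after one missed visit in the US primary PFS analysis and the other analyses that apply it. The excess over the limit is at most 14 days.

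The documents do not support saying that the rule generally removes progressions after one missed visit: in-window on-treatment scans are never affected, and most in-window follow-up pairs stay within the limit under equal weighting. Nor do they support a claim of bias in the hazard ratio. They give no off-treatment rates by arm, and under Protocol Section 5.4 a subject who stops only one drug for tolerability may stay on the other, so stopping venetoclax or placebo alone need not move anyone into response follow-up.

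The estimate of about 0 to 2 of 150 events rests on the assumed 2% to 10% and on equal weighting of scan days. It is a small correction, but it concerns a pre-specified rule for a primary analysis.

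**What to change.** In SAP Appendix 8.1, keep the gap measured from the actual last adequate assessment and allow each scan the protocol window that applies to it: 7 days on treatment, 14 days in response follow-up. The limits stay at 182/210/238/294/350 days when both scans are on treatment. They become 189/217/245/301/357 days when only the progression scan is in follow-up, and 196/224/252/308/364 days when both are. Correct Step 2 and the footnotes that apply 7 days to every visit. State which window governs when the event is a death, since no scan then fixes it.

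The cost is appendix wording and a small programming change that needs the treatment status at each scan. There is one trade-off. A gap rule is lenient after a late last scan. With that scan 14 days late in follow-up, the second visit's window closes at target + 168 + 14 = 182 days on the 12-week schedule. The present limit admits events to 14 + 182 = 196 days; the corrected one admits them to 14 + 196 = 210. That is acceptable for a rule meant to catch clear double misses, but it should be a stated choice. Make the change before unblinding; afterwards it would look driven by the data.
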